AdventHealth Employees: Recruitment efforts will follow AdventHealth recruitment SOPs for research. AdventHealth Employees will not be individually targeted nor excluded from study participation based on employment. AdventHealth employees who engage the TRI asking to participate in the study will be processed per standard consent procedures for participants. In addition, during the consent process, the study staff will review standard consent language stating that an employee's participation or lack of participation in the study will not affect their employment status or relationship with AdventHealth.

Inclusion Criteria

1. Participant must be male or female, ages 60 through 80 years of age.
2. Participant has pre-diabetes or has been diagnosed with type 2 diabetes and taking 0-3 oral hypoglycemic agents, which include basal insulins, incretin mimetics, DPP-4 inhibitors, Sulfonylureas and/or Metformin therapy, and has an Hgb A1C < 9.0%.
 - a. Participants on Insulin, , SGLT2 inhibitors, and Thiazolidinediones will be excluded.
 - b. Pre-Diabetics are defined as having an HgbA1c of greater than or equal to 5.7% and less 6.5%, or a fasting glucose of greater than or equal to 100 mg/dl and less than 126 mg/dl or has a glucose of greater than or equal to 140 mg/dl and less than 200mg/dl at the 2 hour blood draw during OGTT
3. Participant must have renal function with an estimated glomerular filtration rate (eGFR) > 45 ml/min/1.73m² determined at screening.
4. Participant's triglyceride level is < 350 mg/dl and LDL cholesterol is ≤ 150 mg/dl at screening.
5. Participant states willingness to follow protocol as described, the prescribed activity level and completing any forms needed throughout the study.
6. Participant has voluntarily signed and dated an informed consent form, approved by an Institutional Review Board/Independent Ethics Committee, and provided Health Insurance Portability and Accountability Act authorization (HIPAA) or other privacy authorization prior to any participation in study.

Exclusion Criteria

1. Participant has type 1 Diabetes.
2. BMI > 40.0 kg/m²
3. Participant is actively pursuing weight loss and/or lifestyle changes.
4. Participant has a history of pressure ulcers.
5. Participant has a stated history of Deep Vein Thrombosis (DVT), pulmonary embolism, or a known hypercoagulable condition, or other clotting or bleeding disorders.
6. History of gastrointestinal or intracranial hemorrhage.

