21. Participant has an obstruction of the gastrointestinal tract, inflammatory bowel disease, short bowel syndrome or other forms of gastrointestinal disease such as stage III or above gastroesophageal reflux disease, gastroparesis, peptic ulcer disease, celiac disease, intestinal dysmotility, diverticulitis, ischemic colitis and bariatric surgery.
22. Participant cannot abstain from alcohol for the pre-bed rest and bed rest portion of the study. For the recovery portion of the study the participant must agree to consume no more than ~14gm of alcohol per day (equivalent to ~ 1 glass of wine (4-5 oz 12% ABV) or ~bottle of beer (12 oz 5% ABV) /day).

23. Participant cannot refrain from taking medications/dietary supplements/herbals or substances that could modulate glucose metabolism (other than oral hypoglycemic medications), or are considered anabolic, or reduce weight (fat mass), or that may interact with low-molecular weight heparin or induce hypo- or hyper-coagulable state, in the opinion of the PI or medical investigator, starting one week prior to Pre-bed rest phase and over the entire course of the study. These include progestational agents (except prescribed birth control), steroids, growth hormone, dronabinol, marijuana, calcium-beta-hydroxy-betamethylbutyrate (CaHMB), free amino acid supplements and dietary supplements to aid weight loss.
24. Participant has a mini-Mental State Examination score < 21.
25. Subjects who fulfill any of the contraindications for MRI; examples include metal implants, devices, paramagnetic objects contained within the body and excessive or metal-containing tattoos.
26. Unable to participate in MR or DEXA assessments due to physical limitations of equipment tolerances (e.g., MRI bore size and DEXA 450-pound weight limit), claustrophobia, or based on Investigator's judgment at screening.
27. Participant has a sensitivity or allergy to lidocaine.
28. Participant has a sensitivity or allergy to heparin, enoxaparin, or other low molecular weight heparin.
29. History of allergy to pork products.
30. History of heparin-induced thrombocytopenia.
31. Hemoglobin < 10.0 g/dL for females; < 11.0 g/dL for males; or participant has clinically significant signs/symptoms of anemia in the opinion of the PI or medical provider.
32. Concomitant medications with known contraindication or interaction with low-molecular weight heparin (including anti-platelet agents, anti-coagulant agents, non-steroidal anti-inflammatory drugs)

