We will recruit volunteers through public advertisement by placing advertisements in community newspapers and radio, as well as on social media. Individuals who respond to the ads will be contacted by telephone for preliminary screening and will be given an opportunity to ask initial questions and be provided additional description of the study. Potential volunteers who seem to meet criteria will be scheduled for an outpatient examination at TRI. Informed, written consent will be obtained at the screening visit.

We anticipate ~400 phone screens to successfully complete 18 participants per group.

Consent Process

We attest that all study staff delegated the authority to obtain informed consent will follow The institutional "SOP: 401.116 Informed Consent Process and Written Documentation of Informed Consent "and Investigator Guidance: Remote Informed Consent Process in Non-Exempt Research (HRP-831)" and Investigator Guidance: Remote Informed Consent Process in Non-Exempt Research (HRP-831)".

Potential subjects will be given time to read the consent document and will be interviewed by a clinical coordinator. The coordinator will give a detailed overview of the study and then ask if the potential subject has questions and if they might be interested. The candidate is then encouraged to ask questions. After all questions have been addressed and interest remains, the candidate then signs the consent if he/she chooses to do so. After the subject has signed the consent or in the scenario of the remote Inform Consent process once the original signed copy has been received, inclusion and exclusion criteria will be reviewed. The new subject is given a photocopy of the signed consent form for his/her records and the PI/Sub-I will review all participant Inclusion Exclusion Worksheets. Once deemed eligible, the PI/Sub-I will sign and date the Inclusion Exclusion Worksheet. Participants will be free to withdraw at any time for any reason without consequence.

All study staff delegated the authority to obtain informed consent will follow SOP: 401.116 Informed Consent Process and Written Documentation of Informed Consent.
Non-English Speaking Subjects

The participant population that we recruit will be primarily English speaking. In the unlikely event that a non-English speaking participant meets criteria for enrollment, the AdventHealth IRB Investigator Guidance: Short-Form Consent Process in Research (HRP-804), will be followed.

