Capillary blood glucose will be measured four times a day for type 2 diabetics, before each meal and at bedtime. If two consecutive results of $> 240\text{mg/dl}$ are recorded, the study physician will review and change the patient's current treatment regimen (DPP-4 inhibitors, sulfonylureas and/or Metformin) to prevent further hyperglycemia. If two consecutive results of $> 270\text{mg/dl}$ are recorded, the study physician may initiate insulin therapy. Insulin therapy will continue until the participant reaches a target glucose range of 140–180 mg/dL (7.8–10.0 mmol/L). The participant's treatment regimen and diet will be reviewed and changed as necessary to prevent hypoglycemia ($< 70\text{ mg/dL}$), although this is not expected with medications like, DPP-4 inhibitors and/or Metformin.

The following table summarizes the schedule of assessment during Bed Rest.

Assessment	Bed Rest (Days)										
	1	2	3	4	5	6	7	8	9	10	11 (post BR)
Placement of Accelerometers	X	X	X	X	X	X	X	X	X	X	X
Adverse events	X	X	X	X	X	X	X	X	X	X	X
Medication/supplement history	X	X	X	X	X	X	X	X	X	X	
Eucaloric Diet - Adequate protein	X	X	X	X	X	X	X	X	X	X	
Vital signs	X	X	X	X	X	X	X	X	X	X	X
Passive Exercise⁴	X	X	X	X	X	X	X	X	X	X	
Incentive spirometer⁵	X	X	X	X	X	X	X	X	X	X	
Evaluate DVT risk	X	X	X	X	X	X	X	X	X	X	
Body Weight	X		X		X		X		X	X	
Metabolic Body Weight¹⁶											X
Glucose Clamp - 4Hr⁶											X
RMR¹⁰											X
24-Hour Urine											X
Blood draw (hemoglobin and hematocrit)⁷							X				X
Deuterated H₂O administration⁸										X	X
Fasting Muscle Biopsy/Blood draw¹											X
Fasting Adipose Biopsy² (optional)	X									X	
Anticoagulant Therapy		X	X	X	X	X	X	X	X		

DEXA³								X	
MR Assessments (ATPmax/IMCL/IMAT³)								X	
Orthostatic Hypotension Assessment¹¹								X	
VO₂max test									X
400m walk test									X
BiodeX/Strength testing								X	
SPPB								X	
Step Test								X	
Questionnaires⁹									X

¹Muscle Tissue Biopsy: For this study fasted is defined as consuming no food (except for water and allowed medications/dietary supplements) for at least 8 hours the before blood draw/muscle biopsy. Fasting status should be verified verbally with the subject. A venipuncture blood draw will also be taken prior to each muscle biopsy (Approximately 44ml on Day 10)). Blood will be processed, aliquoted and stored at -80C.

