Bed Rest Intervention. The 10-day bed rest intervention will result in a mild deconditioning that may increase fatigability and lower muscle strength (10-20% decrease) and mass (-3% approximately) and increased body fat mass of participants. Individuals with prolonged immobility are at risk for venous thromboembolism (VTE). There is also a risk of pressure ulcers – extrinsic pressure greater than capillary perfusion pressure (30mm/Hg) for a prolonged period of time results in ischemia to the affected tissue. Both hyperglycemia and hypoglycemia are risks for hospitalized patients with T2D and are associated with adverse health outcomes. However, these risks are mitigated by close clinical monitoring during the bed rest intervention (VTE prevention and glycemic control plans) and completion of the exercise recovery program. The participants will be informed that they may abort the study at any time. There are no alternative procedures/methods available with less risk or cost that provide comparable information to that obtained by the procedures described in this proposal.

Enoxaparin. There is a risk of bleeding, nausea, diarrhea, fever, swelling of the hands or feet, and injection site reactions including swelling, pain, bruising, and redness. Concomitant medications with known contraindication or interaction with low-molecular weight heparin (including anti-platelet agents, non-steroidal anti-inflammatory drugs) will be exclusionary.

RMR/RQ. There is no physical risk associated with RMR/RQ. Other risks include a feeling of claustrophobia experienced by some subjects while under the transparent “hood”.

Magnetic Resonance Imaging and Spectroscopy. There are no known biological risks associated with magnetic resonance imaging and spectroscopy. Some short-term discomfort may be experienced. The short-term risks associated with MRI are minimal, but include heating, loud noises and claustrophobia. There are some people who should not undergo MRI; the contraindication is largely based on the presence of metal objects within a person (i.e. pacemaker, aneurysm clip, metal fragments, etc.).

Hyperinsulinemic-euglycemic clamp. There is a risk of hypoglycemia (low blood sugar) during the clamp.

Mitigation of Risks

Blood draws and/or IV (lab samples, e.g.). All venipuncture will be conducted by qualified staff using aseptic techniques. Total blood volume throughout the entire study will be approximately 550 mls.

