Therefore, we will mitigate risk of VTE in our high-risk participant population through prophylactic anticoagulation with low-molecular weight heparin given its safety profile and advantageous dosing frequency (qd vs. BID/TID for LDUH). Participants will receive enoxaparin 40mg subcutaneous injection, daily while immobile, with dose held only on the day of biopsies to minimize risk of bleeding or oozing intra- and post-procedurally. We will employ the daily passive exercise, throughout bed rest.

Every effort to prevent a study-related injury will be taken. If a DVT is suspected, the participant will be assessed by a provider, withdrawn from the study, and instructed to seek emergency treatment immediately. Sources: Prevention of VTE in Nonsurgical Patients - [https://journal.chestnet.org/article/S0012-3692\(12\)60124-X/fulltext](https://journal.chestnet.org/article/S0012-3692(12)60124-X/fulltext)

HIT - [https://journal.chestnet.org/article/S0012-3692\(15\)31496-3/pdf](https://journal.chestnet.org/article/S0012-3692(15)31496-3/pdf)

Pneumonia Prevention

Participants will also use an incentive spirometer 5-10 times (every 1-2 hours) daily to prevent pneumonia.

Glycemic management protocol. Hyperglycemia and hypoglycemia are risks for hospitalized patients with T2D and are associated with adverse health outcomes. To mitigate this risk patients with HA1C < 8.0% will be recruited. In addition, a glycemic management protocol will be administered for type 2 diabetics by the study physician. Capillary blood glucose will be measured four times a day, before each meal and at bedtime. If two consecutive results of > 240mg/dl are recorded, the study physician will review and change the patient's current treatment regimen (DPP-4 inhibitors, sulfonylureas and/or Metformin) to prevent further hyperglycemia. If two consecutive results of >270mg/dl are recorded, the study physician may initiate insulin therapy. Insulin therapy will continue until the participant reaches a target glucose range of 140–180 mg/dL (7.8–10.0 mmol/L). The participant's treatment regimen and diet will be reviewed and changed as necessary to prevent hypoglycemia (<70 mg/dL), although this is not expected with medications like, DPP-4 inhibitors and/or Metformin.

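### The protocol gives two HbA1c entry limits (< 9.0% in the criteria, < 8.0% in the risk section), and inclusion items 2 and 2a do not agree on basal insulin users

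*Protocol*

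**What the plan says.** **HbA1c.** In Inclusion Criteria, item 2, a participant with diagnosed type 2 diabetes qualifies when "taking 0-3 oral hypoglycemic agents, which include basal insulins, incretin mimetics, DPP-4 inhibitors, Sulfonylureas and/or Metformin therapy, and has an Hgb A1C < 9.0" per cent. In Mitigation of Risks, under the glycemic management protocol, the text names hyperglycemia and hypoglycemia as risks and then says: "To mitigate this risk patients with HA1C < 8.0% will be recruited". The next sentence adds a second measure: "In addition, a glycemic management protocol will be administered for type 2 diabetics by the study physician".

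**Insulin.** Item 2 names basal insulins in its list of permitted agents. Item 2a, directly beneath it, reads: "Participants on Insulin, , SGLT2 inhibitors, and Thiazolidinediones will be excluded". The bed rest glucose plan appears in Phase III and again under Mitigation of Risks. It describes the current regimen as DPP-4 inhibitors, sulfonylureas and/or metformin, and says that after two consecutive readings above 270 mg/dl "the study physician may initiate insulin therapy".

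**Who decides eligibility.** Under Consent Process, the investigator or sub-investigator reviews every worksheet: "Once deemed eligible, the PI/Sub-I will sign and date the Inclusion Exclusion Worksheet".

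**The concern.** Both statements about HbA1c describe who will be recruited, and both cannot be true of a person at, say, 8.5%. The lower figure is not offered as background. It is the first measure named against a risk that the protocol acknowledges, and the glucose management plan comes after it as an additional measure. Eligibility is signed off on a worksheet of inclusion and exclusion criteria, so the numbered list is the natural operative text and < 9.0% is the limit most likely to be applied. The protocol then claims a safeguard that it does not deliver. A reader of the risk section, such as an ethics committee or monitoring board member, would believe the cohort to be better controlled than the one the criteria admit.

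The insulin conflict is of the same kind but lies entirely within the numbered criteria. Someone on basal insulin is on a permitted agent under item 2 and on an excluded one under item 2a. Two conscientious readers could decide differently, and either decision could later be called a deviation.

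At stake is whether entry into 10 days of strict bed rest follows one rule, and whether the stated risk mitigation describes the people who are enrolled.

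**Working it through.** The point depends on no sample size, power or error rate, so the check is a comparison of texts. All of it is current protocol text, not an amendment log.

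**Step 1: HbA1c limits side by side.**

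| Place | Limit | Role in the text |
|---|---|---|
| Inclusion Criteria, item 2 | < 9.0% | numbered entry criterion |
| Mitigation of Risks, glycemic management protocol | < 8.0% | measure against hyper- and hypoglycemia |

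Difference: 9.0 − 8.0 = 1.0 percentage point. For a person with type 2 diabetes:
- below 8.0%: both texts agree that the person may enter;
- from 8.0% to below 9.0%: eligible under item 2, outside the population described in the risk section;
- 9.0% or above: both texts agree that the person may not enter.

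Pre-diabetes does not widen the problem where it is defined by HbA1c, since that definition stops below 6.5%. Nothing elsewhere in the protocol reconciles the two limits.

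**Step 2: is < 8.0% part of the management plan or separate from it?** The plan is introduced as something done in addition to recruiting below 8.0%. The two are therefore separate layers, and running the plan does not by itself fulfil the recruitment statement.

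**Step 3: basal insulin.**

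| Text | Reading for a basal insulin user |
|---|---|
| Item 2 | permitted; basal insulins are listed among the 0–3 agents and called oral |
| Item 2a | excluded; insulin is named with no basal exception |
| Bed rest glucose plan | insulin is something to start, which suggests that participants arrive without it |

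Item 2a is a sub-item of item 2. A participant who must satisfy the whole item fails at 2a, so the text leans toward exclusion, and the bed rest plan leans the same way. Two things keep this from being settled. The specific mention of basal insulins in item 2 can be read as a carve-out from the general word in 2a. Item 2a also has a gap between two commas straight after the word insulin, where a term may have been removed or lost. The word insulin stands complete before the first comma, so the conflict probably does not depend on the missing term, but a qualifier there cannot be ruled out.

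**Step 4: what limits the harm.** In bed rest, capillary glucose is measured four times a day in type 2 diabetics. Two consecutive results > 240 mg/dl trigger a review and change of treatment, and two > 270 mg/dl allow insulin to be started. None of this depends on entry HbA1c. The Bed Rest Intervention paragraph of Potential Risks relies on this layer: "However, these risks are mitigated by close clinical monitoring during the bed rest intervention (VTE prevention and glycemic control plans".

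**The case against.** The strongest reply is that little turns on this in practice. The study has one site, and the investigator or sub-investigator reviews every worksheet, so divergent application is less likely than in a multi-site trial. Monitoring and the glucose action rules cover everyone with type 2 diabetes, and the risk paragraph on bed rest cites monitoring and glycemic control plans rather than an HbA1c cap. Item 2a, read as part of item 2, already points one way. All of this stands, and it limits the consequence. It does not make the two HbA1c limits compatible, and it does not tell staff whether basal insulins were meant to be allowed.

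A reader might be tempted to infer more than the protocol supports:

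- **That < 8.0% is the true limit.** The protocol does not say which figure is intended. The regimen list in the risk section is narrower than the one in item 2, since it also omits incretin mimetics. That is compatible with the risk section being the text that was not updated.
- **That people at 8.0–8.9% would be unprotected.** They would not be, because the glucose checks and action rules apply to them in full.
- **That exclusion 23 settles the insulin question.** It bars "substances that could modulate glucose metabolism (other than oral hypoglycemic medications" and so seems to leave insulin outside the exemption. But item 2 itself counts basal insulins as oral hypoglycemic agents. In the protocol's own vocabulary they may already be exempt, so exclusion 23 is no firm evidence either way.
- **That the number of people affected can be estimated.** No HbA1c distribution is given, nor the mix of pre-diabetes and type 2 diabetes. Any headcount would only restate an assumed share.

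**Conclusion.** The point holds and should be fixed. The HbA1c conflict is plain: two recruitment limits 1.0 percentage point apart, with nothing to reconcile them. The conclusion that the safeguard is dropped assumes that the site works from the numbered criteria. If staff instead apply < 8.0%, they are using a limit that is not among those criteria. The insulin conflict is less certain. Exclusion is the more natural reading, but only the sponsor can say what was meant.

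The effect is on consistency of eligibility and of the stated safety measures, and it is bounded by the monitoring that applies to all participants with type 2 diabetes.

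**What to change.** **HbA1c.** State one limit in both places. There are two ways:
- change item 2 to < 8.0%, so that the stated mitigation holds; the cost is possibly slower recruitment, because people from 8.0% to below 9.0% no longer qualify;
- if < 9.0% is the intended limit, change the figure in the glycemic management text to < 9.0%; who is enrolled under the criteria does not change, and the risk section then describes them correctly.

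**Insulin.** Make items 2 and 2a agree, in one of two ways:
- delete basal insulins from the list in item 2, which fits the plain wording of 2a and the bed rest plan;
- if basal insulin is to be allowed, have 2a exclude insulin other than basal insulin.

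While editing 2a, restore or remove whatever belongs in the gap after the word insulin.

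The cost is an amendment to the wording and a matching worksheet. The sample size and the analysis stay as they are.

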¹³A 400-meter walk test at usual pace will also be conducted. The 400-meter walk test is a measure of cardiorespiratory fitness, lower extremity muscle function and general mobility. During this self-paced walking test, patients are instructed to walk 400 meters at their usual pace or without any expectation of time. The ability to walk 400 meters in less than 15 minutes has been suggested as an indicator of sufficient capacity for community ambulation. The goal of this outcome measure is to determine the amount of time required to walk 400 meters. The patient may rest whenever necessary but should understand the aim is to walk the entire 400-meter distance as soon as possible. The time needed to complete the test will be recorded on source documentation. If the person is unable to walk the full 400 meters because of needing to stop or not completing the distance within 20 minutes, the distance (in meters) and time walked during the test will be recorded.

The 400mwt should be performed using a 20 m course. The 400-meter walk test will be performed and timed using a stopwatch. Subjects will be instructed to walk as quickly as possible for 10 laps around markers placed 20 meters apart. Standard encouragement will be given by study personnel after the completion of each lap.

¹⁰Subjects will perform a hand grip test that will be conducted three times with 1 minute of rest between each repetition using the dominant arm. The greatest grip strength and the average of the three tests will be recorded.

¹¹Vital signs consist of body temperature, pulse rate (or heart rate), blood pressure, and respiratory rate.

¹²A number of health questionnaires will be administered at screening, including: CHAMPS Physical activity, Life Space, Lifestyle, Functional Status, Pittsburgh Fatigability Scale.

¹⁵The Step Test is conducted by recording the time it takes for a participant to complete a series of repeated steps. The participant will be asked to complete a timed step test where they will be repeatedly stepping up and down from an 8-inch high step.

¹⁶Body Weight is Metabolic Weight. Metabolic weight is completed during fasting and with an empty bladder while wearing a gown and underwear. An average weight between two measurements will be used. The metabolic weight will be the difference between the average subject weight and weighted gown.

Screening Visit 2

Approximate visit time: ~ 2 1/2 hours

⁹Resting Metabolic Rate/Respiratory Quotient (RMR/RQ): Indirect calorimetry will measure the resting metabolic rate/respiratory quotient (RMR/RQ) and substrate utilization after an 8-hour overnight fast using a MAX II Metabolic cart (AEI Technologies, Pittsburgh, PA). The analyzer will be calibrated before each subject with standardized gases containing 5% CO₂, 21% O₂ and balance N₂. Subjects will be instructed to lie in a Semi-Fowler's position and remain motionless and awake during these periods. A transparent plastic hood connected to the device will be placed over the head of the subject. Calculations of O₂ consumption (VO₂) and CO₂ production (VCO₂) will be made by comparing a single measure of the O₂ and CO₂ concentrations of the testing room to continuous measurements of O₂ and CO₂ concentrations in expired air diluted in a constant air flow (20-50 L/min) generated by a pump. From the above, energy expenditure standardized for temperature, pressure, and moisture will be calculated at one-minute intervals.

⁸Graded exercise testing: Volunteers must pass the medical screen before they will be allowed to undergo the exercise test. If the resting ECG prior to the exercise test shows clinically significant abnormalities, the test will not be conducted. If abnormalities develop during the test, the test will be stopped. On both occasions, the participant will be referred to their Primary Care Physician for further evaluation. Before and after exercise activities are performed, the participant's that are type 2 diabetics will have a blood glucose checked using their home glucose monitor or glucose monitor at TRI. Blood glucose will be measured prior to and immediately following each exercise session for safety. If blood glucose is > 300mg/dl, study team will notify TRI provider immediately for review of glucose values, as well as medications. If the glucose values are consistently > 400mg/dl, participant will be instructed to follow up with their primary care physician. If blood glucose is < 100mg/dl, a snack will be given, and the participant will be allowed to exercise. Self-monitored blood glucose measurements should be checked anytime a patient has symptoms of hypoglycemia or hyperglycemia.

Aerobic fitness will be determined by measuring maximal O₂ consumption (VO_{2max}) during a stationary bicycle exercise test. Provider monitoring will follow The American

College of Sports Medicine's (ACSM) Guidelines for Exercise Testing and Prescription. Heart rate, blood pressure and ECG, if applicable, will be recorded throughout this test. During the test, subjects will breathe through a low resistance mouthpiece and wear a nose clip. Expired gases will be measured by indirect calorimetry and heart rate monitored by a portable heart rate monitor and/or ECG.

Following a standardized warm up, subjects will begin exercising at a moderate intensity with the workload (resistance on a cycle ergometer or speed and grade on a treadmill) increased every minute until the subject can no longer continue. VO₂ max tests will take as little time as possible in order to ensure that test termination is due to the subject reaching VO₂ max rather than terminating the test due to muscle exhaustion. A leveling-off (plateau) or decline in oxygen uptake should be demonstrated in order to be reasonably sure that a subject has achieved the maximum capacity for aerobic metabolism. However, there are several additional criteria that will be used to determine if maximal aerobic capacity is achieved. These criteria are: the respiratory exchange ratio (RER) increased to 1.10 or higher and the subject's heart rate increased to within 10 beats of the age-predicted maximum (208 – [0.7 x age]).

The test will also be stopped, and subjects excluded from further participation if there is >2mm ST-segment depression on ECG or evidence of cardiovascular instability, such as hypotension, dangerous arrhythmias or angina.

Prior to beginning the exercise test, the Borg Rating of Perceived Exertion (RPE) Scale will be presented to participants. The RPE Scale is a rating of how hard a person feels their body is working and is an accepted supplementary tool for prescribing exercise programs in both healthy and special populations. Throughout the test, participants will be asked to point to the numerical rating of how they feel and will be encouraged to remember a rating of how "somewhat hard" (13) feels. The rating of "somewhat hard" should coincide with a heart rate of approximately 50-70% of their maximal exertion level. During maximal testing participants should report a rating of 19-20 ("maximal exertion"). A cardiologist will review the ECG, if the medical Provider deems necessary. If a study physician or cardiologist identifies any artifacts observed from the exercise test that may render the participant ineligible for participation in an exercise intervention, that subject will be referred to his/her Primary Care Physician (PCP) or cardiologist for follow-up care and further examination of test results. If participants are referred for further examination, a written approval to perform unsupervised exercise must be obtained by PCP or cardiologist in order for subject to continue participation in the research study. If written approval from the PCP or cardiologist is not able to be obtained, participant will be excluded from further participation in the investigation. The test will take approximately 30-40 minutes.

Accelerometers to assess free-living physical activity over approximately 5 days will be provided, along with instructions on how to use the devices. They will be placed on the arm and wrist. The device will be returned by the participant after at least 5 days of recording and prior to Pre-Bed Rest Day 1.

Phase II – Pre-Bed Rest (PBR).

This phase of the study should be initiated no more than 35 days after the first screening visit. PBR 1 will be considered the study baseline. The Table below summarizes the schedule of assessment during Pre-Bed Rest.

The five days prior to bed rest is considered the pre bed rest period and will be abbreviated as PBR 1 to PBR 5. Subjects will be required to report to the study site for meals and assessments during these 5 days. To prepare subjects for the bed rest diet (stabilize diet), subjects will be provided with a breakfast, lunch and dinner, for consumption at the study site or as packaged meals for each of the 5 days. Subjects will consume breakfast at the study site and will have the option to consume lunch and dinner at the study site, or they will be provided with a packed lunch and dinner for later consumption.

The metabolically balanced study diet will be formulated for each subject to have each subject's protein intake equal to 0.8g/kg body weight/d, and kcal intake to be based on their measured total daily energy expenditure from the armband accelerometer. The remaining macronutrients will be distributed approximately to the subject's typical diet from the 3-day food diary.

Body Weight during the Bedrest phase only, will be taken using the bed scale during fasting and with an empty bladder while wearing a gown or light clothing and undergarment(s).

Assessment	Pre-Bed Rest (days)				
	1	2	3	4	5
Medication changes	X	X	X	X	X
Metabolic Body Weight ¹⁶	X	X	X	X	X
Evaluate DVT Risk					X
MR Assessments ¹ (ATPmax//IMCL/IMAT/)		X*			
Biodex/Strength assessment ²			X*		
DEXA ³			X*		
Eucaloric Diet Stabilization - Adequate protein	X	X	X	X	X
Admit patient for bed rest intervention					X

*The imaging and exercise procedures may be performed as baseline measurements on any Pre-Bed Rest day

¹MR Assessments to occur preferentially on PBR2, however may occur on any PBR day to accommodate scheduling. Assessments defined below:

Maximal ATP Production (ATPmax): ATP_{max} will be measured in order to determine in vivo mitochondrial capacity. Participants will complete the MR Screening for ATP_{max}, and

the information will be verified with the participant by a member of the TRI Imaging Core to determine if data acquisition can be performed safely. The magnetic resonance scans to measure mitochondrial energetics will be performed on a 3T Philips Acheiva at the TRI. The participant will be informed that the imaging scans will produce loud “knocking” noises, but they will be provided both ear plugs and earphones to minimize this noise.

OVERVIEW: The Phosphocreatine (PCr) recovery time constant (τ) and the PCr level in oxygenated muscle at rest (PCr_{rest}) will be used to calculate maximum mitochondrial capacity (ATP_{max}). Participants will be asked to lie supine on the patient table of the MRI for approximately up to one hour. After set of survey images is acquired to locate the muscle group of interest, a fully relaxed ^{31}P spectra will be collected. The ATP_{max} experiment will be performed by obtaining a set of sequential ^{31}P spectra; one spectrum will be acquired every 6-7.5 seconds for the duration of the ATP_{max} experiment. For the first two minutes, the participant will remain still in order to obtain baseline [PCr], [ATP] and [Pi] measurements. After the baseline is established, the participant will be asked to perform contractions of the quadriceps (by kicking against straps around the lower leg) for up to 45 seconds. After kicking is stopped, the participant will remain still for the remainder of the experiment in order to allow the PCr peak to return to baseline. The ATP_{max} experiment may be repeated. The scan time for the ATP_{max} experiment will take approximately 45 minutes.

Intramyocellular Lipid *In Vivo* ^1H Magnetic Resonance Spectroscopy (IMCL): The participant will be asked to lie supine on the patient table of the magnet (Philips Acheiva 3T) for approximately 45 min. The participant’s leg will be positioned inside a radio frequent (RF) ^1H knee coil with the knee in extension and the ankle in a neutral position. Standard clinical MR Imaging, including 3-place localization and T2 weighted images, will be completed to obtain anatomical images for voxel / slice localization. The PRESS (point resolved spectroscopy) sequence with water suppression will be used to obtain spectroscopic measurements of the intramyocellular lipid (IMCL). A PRESS single voxel sequence will be used to obtain spectra from separate voxels (up to $15 \times 15 \times 15 \text{ mm}^3$) within largest volume of the calf muscles (echo time (TE) = 35 msec and a resonance time (TR) = 1500 seconds). Voxels will be positioned to avoid fascia, vascular structures and gross marbling as determined using the anatomical images.

MR assessment of Intramuscular and Subcutaneous Fat (IMAT): Volumetric measurement of fat, muscle and bone in the participant’s mid-thigh leg will be completed using an Achieva 3T MRI/Multinuclear MRS (Philips, Andover MA). Scans will be performed under standardized conditions with subjects in a supine position. The torso XL coil will be placed around their legs (encompassing both knees and thighs). If the participant and the coil cannot fit into the bore of the magnet, the coil will be removed and the exam will be completed using the quadrature body coil. Each scan will take approximately 30 minutes to perform. Low resolution scans will be taken to determine the approximate midpoint of the participant’s femur. Then T1 weighted imaging sequences will be performed centered at the midpoint.

²Strength assessment. The initial weights for knee extension should be set based on the subject's predicted 1 repetition maximum (1 RM). Based on previous research, males and females < 65 years of age have a predicted 1 RM of 90% and 60% of their body weight, respectively, for the knee extension. For each additional 10 years of age the 1 RM should decrease 10% (ex. 91-year-old male would have a predicted 1 RM of 60% of his body weight). This number should be calculated and recorded on the data collection sheet. One can then calculate the subject's first 4 lifts at 20, 35, 50, and 70 percent of predicted 1 RM. This weight scale is followed, and weight is continually increased until termination of the test. If, prior to exercise, the blood pressure is less than 160/100 mm Hg, then the subject will warm-up on a bike for ~ 1 minute with no resistance. If BP is elevated the subject should rest for 3 more minutes. If BP is still elevated greater than 160/100 mm Hg, the subject will be sent home with the recommendation to contact their physician, and this subject will be followed up for potential re-testing.

Termination criteria for maximal strength testing:

- A subject asks to discontinue testing.
- An individual moves a weight through a full range of motion with relative comfort but cannot move through the full ROM with a two-unit increase.
- Subject cannot move through full ROM with proper form (subject lifts lower or upper back away from padded seat, subject kicks pad using acceleration force to lift weight, hands not crossed across chest, uneven or jerky ROM).

Relative termination criteria:

